We will recruit peer mentors by contacting facilitators of LBD support groups and asking them to distribute IRBapproved recruitment fliers, placing recruitment fliers in the waiting area of Rush University's Parkinson's and Movement Disorders Program (including locations at Rush University Medical Center, Rush Copley, and Rush Oak Park, given the presence of movement disorders specialists at each location), distributing recruitment fliers at community events, asking national organizations such as the Parkinson's Foundation and the Lewy Body Dementia Association to distribute recruitment fliers by mail, email or social media, asking national organizations such as the Parkinson's Foundation and the Lewy Body Dementia Association to post a social media recruitment survey on social media platforms such as Facebook and Twitter that interested and eligible individuals can complete to indicate their potential interest in studies of caregiver peer mentoring, sending potential participants the recruitment flier via MyChart , contacting individuals referred to the program by providers at Rush or other institutions in the Chicago area, and contacting mentors and mentees who participated in the previous mentor program who might be interested in serving as a mentor in this program. Interested participants will be given study information and screened for eligibility to exclude potential mentors who do not meet inclusion criteria, who express discomfort discussing sensitive topics with their potential mentee (including, but not limited to, challenges faced in their own caregiving journey, advance directives, or cultural differences between the mentor and mentee), or whose expressed belief systems would suggest inability to deliver the curriculum.

Mentors will attend one 6-7 hour training session, either held in-person at Rush University or a via passwordprotected videoconferencing application, such as Zoom. Study expectations and logistics will be reviewed with each potential mentor prior to the training session via phone. For all subjects, regardless of whether they attend an online or in-person training session, the informed consent process will take place online via REDCap prior to the training session date. In this way, participants can contact the study team with any questions or concerns prior to the training session. After participants have read the online consent form and indicated they are willing to participate, they will complete capacity assessment questions (see Section V.b.) to ensure understanding of the consent process.

Individuals may refuse to participate in the study and leave the peer mentor training session at any time. At the beginning of the training session, baseline data will be collected either via printed pen-and-paper assessments, or via online surveys (demographics, mentoring preferences, mastery scale, LBD knowledge test, Dementia Attitudes Scale (DAS); see Section III.d. for details). Next, mentors will receive training regarding topics including active listening, mentoring, goal-and boundary-setting, an overview of LBD, risk factors for hospitalization, impact on caregiver, practical approaches to symptom management, and caregiving issues. The study team will then present the new PERSEVERE curriculum and accompanying handbook. The study team will solicit questions and lead role-play conversations. Finally mentors will complete post-training assessments (mastery scale, LBD knowledge test, DAS) and will receive a training stipend (either directly from study team members if in-person, or mailed/emailed if completing training virtually).

III.c. Aim 3: Subject Identification, Recruitment, Consenting and Study Procedures

We will recruit caregiver mentees by contacting facilitators of LBD support groups and asking them to distribute IRB-approved recruitment fliers, placing recruitment fliers in the waiting area of Rush University's Parkinson's and Movement Disorders Program (including locations at Rush University Medical Center, Rush Copley, and Rush Oak Park, given the presence of movement disorders specialists at each location), distributing recruitment fliers at community events, asking national organizations such as the Parkinson's Foundation and the Lewy Body Dementia Association to distribute recruitment fliers by mail, email or social media, asking national organizations such as the Parkinson's Foundation and the Lewy Body Dementia Association to post a social media recruitment survey on social media platforms such as Facebook and Twitter that interested and eligible individuals can complete to indicate their potential interest in studies of caregiver peer mentoring, sending potential participants the recruitment flier via MyChart, and contacting individuals referred to the program by providers at Rush or other institutions in the Chicago area. A study team member will call interested caregivers to provide them with study

information and logistics by reading from an IRB-approved recruitment script. If interested, the team member will email the caregiver a link to the electronic informed consent and baseline survey in REDCap. The components of the informed consent document will appear on the first page of the online survey. Potential participants must read through the informed consent language on the first page and click a button agreeing to continue. On the next page of the survey, we will incorporate capacity assessment questions to ensure understanding of the consent process. Upon correct completion of these questions, the participants will be directed to begin the actual survey questions. Participants will be asked to complete a demographics survey, a survey describing the characteristics of the LBD patient for whom they are caring, and a mentoring preferences survey to facilitate matching (see Section II.d. for details). As recruitment for mentees will be rolling and occurring during mentor recruitment and training, there may be lag time between ICF completion and mentoring intervention of weeks to months, and this will be clearly communicated to participants during the screening phone calls and reiterated in the ICF.

Once Aim 2 (above) is complete and 36 mentors have been trained, caregiver mentees will be matched with mentors by relationship to LBD patient, then by sex and age, as much as possible. Mentor and mentee preferences expressed in the mentoring preferences survey will be honored to the extent that the study team is able given the available mentor and mentee participants. The study team will contact mentees once a match is available for them. First, the study team will direct the mentee to complete baseline primary and secondary outcome assessments online via REDCap, including: mastery scale¹⁹, LBD knowledge test, loneliness scale⁴¹, Short Zarit Burden Interview (ZBI-12)⁴², Hospital Anxiety and Depression Scale (HADS)⁴³, Geriatric Depression Scale – Short Form (GDS-SF)⁴⁴, and Dementia Attitudes Scale (DAS)⁴⁵ in order to obtain their pre-intervention baseline. The study team will then provide the mentee with contact information for their mentor, and caregivers will be mailed the PERSEVERE handbook.

Mentor-mentee pairs will then begin the 16-week peer mentor program. During this time, pairs will be expected to speak for ≥15-30 minutes weekly, and to review that week's PERSEVERE topics in the handbook before or during each call to facilitate meaningful conversations. Discussions are not scripted and will not necessarily be limited to that week's topics, at the discretion of the participants. Mentors and mentees will complete online study diaries every 2 weeks, assessing intervention fidelity. Up to 3 email reminders will be sent and/or up to 3 phone calls attempted to complete each study diary. Diary entries will include information such as call frequency, duration, topics discussed, and concerns. At the Week 8 or Week 10 survey, all mentees and those mentors who are still actively caregiving for a loved one with LBD will complete the Parkinson's Disease Carer Questionnaire (PDQ-Carer), a novel measure of PD-specific caregiver quality of life. Mentors will participate in 4 recorded monthly conference calls to share successes, challenges, and feedback, and to ask questions of and be supported by the study team.

Upon completion of the 16-week mentor program, mentors and mentees will be sent a link to complete postmentoring assessments online (mentors: mastery scale, LBD knowledge test, DAS, PDQ-Carer; mentees: mastery scale, LBD knowledge test, loneliness scale, ZBI-12, HADS, GDS-SF, DAS, PDQ-Carer, and fall frequency and healthcare utilization of their loved one; see Figure 3).

	Aim 2 - Mentor Training	Aim 3 – PERSEVERE Pilot
Primary	 Mastery scale¹⁹ 	Mastery scale
Outcomes	Multiple-choice LBD	 LBD knowledge test
	knowledge test	 Loneliness scale⁴¹
Secondary	Mastery Scale (after	 Short Zarit Burden Interview (ZBI-12)⁴²
Outcomes	mentoring)Dementia Attitudes Scale	 Hospital Anxiety and Depression Scale (HADS)⁴³
	 (DAS)⁴⁵ Parkinson's Disease Carer 	 Geriatric Depression Scale – Short Form (GDS- SF)⁴⁴
	Questionnaire (PDQ-Carer)	• DAS

Figure 3. Outcomes, Fidelity Metrics, Covariates, and Confounders in Aims 2 &

	(only if actively caregiving for loved one with LBD)	 Parkinson's Disease Carer Questionnaire (PDQ-Carer) 	
Fidelity Metrics		Frequency and duration of calls	
		 Number of missed calls/weeks 	
		 Coverage of target topics; other topics discussed 	
		Qualitative feedback in mentor conference	
		calls	
		 Dropout rate and reason 	
Demographics,	Sex, age, race, ethnicity, education, comorbidities, caregiving relationship, duration of		
Confounders,	caregiving; patient's disease duration, stage, ADLs ⁴⁶ and IADLs ⁴⁷ at baseline, and		
Covariates	patient's monthly frequency of falls and acute healthcare utilization (combined		
	number of ER visits not yielding admission + hospital nights) in the months prior to and		
	during the intervention.		

III.d. Assessments

All participants who agree to be part of the study and sign the informed consent form will be asked to complete a series of surveys and assessments. There is no known risk associated with completion of these assessments. All or some of the following measures may be administered but are not limited to:

- Mastery Scale: A 7-item scale measuring the extent to which a participant sees life as being under his/her personal control vs. something that is fatalistically ruled. Scores range from 7 to 28, with higher scores indicating greater levels of mastery.¹⁹
- LBD Knowledge Test: A multiple-choice test created by the study team to assess participants' level of knowledge of LBD. Higher scores indicate a greater degree of knowledge of LBD and its effects. This assessment will be based on the revised PERSEVERE curriculum following the conclusion and analysis of data from focus groups.
- Dementia Attitudes Scale (DAS): A validated, 20-item scale measuring participants' attitudes toward dementia and individuals with dementia. Scores can range from 7-140, with higher scores indicating more positive attitudes.⁴⁵
- Loneliness Scale: A 3-item, validated measurement of a participant's feelings of isolation or disconnectedness. Scores can range from 3-9, with higher scores indicating greater loneliness.⁴¹
- Short Zarit Burden Interview (ZBI-12): A 12-item, validated measurement of caregiver burden in older adults. Scores range from 0-48, with higher scores indicating greater caregiver burden.⁴²
- Hospital Anxiety and Depression Scale (HADS): Brief, 14-item highly validated scale for measuring anxiety (7 items) and depression (7 items), where scores of >8 for either anxiety or depression indicate probable symptoms.⁴³
- *Geriatric Depression Scale Short Form (GDS-SF):* Brief, 15-item, highly validated scale for measuring depression in older adults, total possible range of 0-15, where a score >5 suggests depression⁴⁴.

- Mentoring Preferences Survey: A survey designed by the study team, with input from focus group or interview participants (see Aim 1) that will allow for mentors and mentees to indicate matching preferences (e.g., matching with a person who likes to speak in the evenings vs. the morning, matching with someone of a specific gender, etc.)
- Katz Index of Activities of Daily Living: A brief, 6-item assessment that indicates the level of assistance with ADLs needed by patients for whom mentees are caring⁴⁶.
- Lawton-Brody Instrumental Activities of Daily Living Scale: an 8-item assessment that indicates the level of assistance with IADLs needed by patients for whom mentees are caring⁴⁷.
- Parkinson's Disease Carer Questionnaire: a 29-item, validated assessment measuring 4 domains of quality of life specific to unpaid/family caregivers of individuals with Parkinson's Disease (Jenkinson et al 2012, Jenkinson et al 2013).

III.e. Data Analysis and Data Monitoring

- Ι. Statistical analysis: The primary data will be entered into a HIPAA-compliant database (REDCap)⁴⁸, with quarterly audits for fidelity. Data will be exported to Stata 15 for analysis. Primary and secondary outcomes, covariates and confounders, and fidelity metrics are listed in Figure 2.
- II. Aim 1 (focus groups/interviews, PERSEVERE curriculum development): We will describe baseline demographics of focus group participants, transcribe recordings, and develop a theme codebook. Framework analysis⁴⁹ will be used to guide the revision of the structured, 16-week mentoring curriculum, with provision of practical checklists, goal setting, and step-by-step guides for key areas of LBD caregiving mastery in addition to social support. Several topics in the revised curriculum will be repeated or given two weeks to allow for reiteration in the event of missed mentoring calls.
- III. Aim 2 (peer mentor training, LBD caregiver mastery): We will describe the demographics, baseline mastery, LBD knowledge, and dementia attitudes of mentors pre-training, assessing for normality and reporting means/standard deviation or medians/interquartile range. We will compare within-subject change in mastery, LBD knowledge, and DAS pre- and post-training (primary outcomes) and pre-training and post-mentoring (secondary outcomes) using paired t-tests or Wilcoxon sign rank test, as appropriate.
- IV. Aim 3 (caregiver peer mentoring): We will analyze data fidelity by summarizing categorical variables by frequencies and percentages and will assess continuous variables for normality, summarized by mean/standard deviation or median/interquartile range. We will describe the baseline demographics, patient characteristics (including fall frequency and acute healthcare utilization), mastery, LBD knowledge, loneliness, ZBI, HADS, GDS-SF, and DAS of caregivers. Bivariate analyses will compare change between baseline and 16 weeks of mentoring in each of the above, using paired t-test or Wilcoxon sign rank, as appropriate. We will also compare change in PDQ-Carer between mid-study and Week 16 as an exploratory outcome. To examine potential covariate effects, we will run a series of repeated measures ANCOVAs for pre- and post- primary and secondary outcome measures using demographic and confounder variables as nuisance variables. These analyses will be considered exploratory due to the loss of degrees of freedom resulting from the covariates. Mentor program fidelity metrics including *dropout* rate and reasons, time spent on phone calls, number of phone calls, and topics discussed will be calculated

based on responses obtained from biweekly online study diary entries. Qualitative data will be gathered from the monthly mentor conference calls via notes taken by the study team; framework analysis will be applied to identify key themes regarding successes, challenges, and recommendations for improving the program.

V. Monitoring and Oversight: PERSEVERE will be maintained by the Principal Investigator. The Principal Investigator will review study procedures annually and report any concerns in the IRB continuing application. This is a Level I, Low, Minimal Risk study; therefore, there is minimal risk of unanticipated problems with the exception of breaches in confidentiality. The data for the study will be entered into a secured database using an electronic data capture program such as Research Electronic Data Capture (REDCap)⁴⁸. The database will be stored on a secure password-protected server and not on individual desktop computers. The code sheet will be password protected and the password will be updated annually. Breaches of confidentiality will be reported to the IRB immediately with the "Reportable Event/Unanticipated Problem Form." The PI, co-investigators, and/or study staff will review all data collection forms on an ongoing basis for data completeness and accuracy as well as protocol compliance. The data will be reviewed on a quarterly basis for: Subject accrual (including compliance with enrollment criteria); Status of all enrolled subjects; Adherence data regarding study activities and procedures. Any issues noted during the quarterly data and safety monitoring reviews will be submitted to the IRB annually. Safety data (AEs and SAEs) will be reported to the Principal Investigator and reviewed per occurrence and in accordance with the IRB's regulations. Any significant findings (i.e. protocol deviations) will be reported to the IRB in accordance with requirements and will be documented accordingly. There are no predefined stopping rules for the overall study.

III.f. Data Storage and Confidentiality

All research data files will be stored at the Rush University Parkinson's Disease and Movement Disorders Program in secured file cabinets, including case report forms, informed consent forms and informed consent documentation checklists, and de-identified notes taken by the study team during the focus groups and interviews, mentor training, or mentor program conference calls. Hard copies of case report forms and informed consent documentation checklists will be labeled with the study ID only and maintained in individual files by study ID number. Signed informed consent forms, containing subject names, will be stored separately in the regulatory binder, which will be stored in a locked file cabinet in the PI's office. The notes taken by the study team will be reviewed for any errant identifying data on a monthly basis and censored, and the original hard copies of such notes will be stored in a locked file cabinet in the PI's office.

All subjects (focus group/interview participants, mentors and mentees) will be assigned unique ID numbers.

Only the PI, Co-investigators and research staff will have access to the database. During the consent process, the potential participant will be informed that aspects of their PHI will be shared with collaborating researchers at Rush; however, they will have an opportunity to decline having their PHI shared and still participate. Data will be stored in a format suitable for research inquiries by the PI and Co-Investigators, who might make use of the data in a retrospective manner for other Rush-based research studies. The data collected from this study is restricted to access by the PI and direct study collaborators at Rush. No collaborator will be allowed to share the data outside the study team without the PI's written approval. Collaborators interested in using the data outside of this study will be required to provide a written request to the PI noting the specific data fields of interest, a description of how the data will be used and who will have access/use the data. The PI reserves the right to grant/deny approval to any collaborator prior to the release of any study data. If a particular researcher/collaborator has an interest in a

study population, then the PI will review the database to identify eligible subjects that meet the study inclusion criterion and the potential participant(s) will then be contacted by a member of this study team whom the subject has already met to see if they are interested in participating in the particular study. If a participant is interested, he or she will be referred to that Rush study team and will be scheduled for a separate consent procedure with the individual Rush researcher for that particular study and at that point the participant can choose whether to participate or not in that particular study. The results of this study may be published in a book, journal, and other media or used for teaching purposes. However, all published data will be made anonymous.

IV. Risk/Benefit Assessment

IV.a. Risk

There are no known risks from the completing the surveys and assessments that we will use in this study. Subjects completing these types of surveys and assessments may experience mild boredom or cognitive fatigue. Subjects participating in the focus groups or training session may also experience mild boredom or cognitive fatigue. There is a risk of loss of confidentiality by participating in this study, however the study team will take all reasonable precautions to secure the data and maintain confidentiality as described above. Due to the nature of focus groups and group training sessions, confidentiality of information shared cannot be guaranteed; however, the study team will emphasize to all participants that any information discussed should not be shared outside the group. Mentors will be instructed during mentor training about the importance of confidentiality of mentoring conversations, and this will be reiterated in the handbook for both the mentors and mentees.

IV.b. Potential Benefit to Subjects

Focus group or interview participants: The potential direct benefits to focus group participants include the satisfaction of having contributed to scientific knowledge about LBD and related disorders that may help to improve the quality of life for themselves and other subjects' loved ones with movement disorders. For participants who were previously involved in other support groups or mentor programs, the focus groups may provide positive social interactions with other caregivers and feelings of validation.

Caregiver peer mentors: The potential direct benefits to caregiver peer mentors include validation of their lived experiences and accumulated knowledge as caregivers to a loved one with LBD, providing some potential degree of closure or purpose. Caregiver peer mentors may have previously been involved with other caregivers but become disconnected if/when their loved one with LBD passed away, and by attending the mentor training session, establishing a mentoring relationship, and participating in conference calls, may rejoin the caregiver community and derive benefits from social interactions and shared experiences.

Caregiver mentees: The potential direct benefits to mentees include increased mastery due to the relationship and discussions held with their mentor, decreased depression, anxiety, and caregiver strain due to the positive relationship with emotional support from a caregiver peer mentor.

All subjects: All subjects' involvement will contribute to scientific knowledge determining whether a formal, 16week mentoring program can have an impact on caregiver mastery, strain, anxiety, and depression. This study and future studies may provide a model of care to improve quality of life and caregiver strain for hundreds of thousands of individuals with LBD and related disorders.

V. Subject Consent

V.a. Process of Consent

All focus group and mentor program participants will complete the informed consent process online via REDCap after the study is explained to them and questions are answered by a member of the study team. Informed consent must be completed prior to any participant joining any portion of the study (focus groups, mentor training, or beginning the peer mentor relationship). Participants will be asked to give online consent for the study by trained study team members (PI or co-investigators, the latter of which will be trained by the PI in the process of assessing capacity and obtaining informed consent). Subjects completing the online recruitment survey will follow a link posted to social media by national organizations such as the Parkinson's Foundation and the Lewy Body Dementia Association. Before providing consent, online survey participants will be given the contact information of the study team and asked to contact the team if they have any questions before providing consent. Subjects are not expected to have cognitive impairment, however, subjects may be elderly and at risk of agerelated cognitive changes, so all subjects will be assessed for capacity to consent. The study team has prior experience building capacity assessments into REDCap online surveys.

V.b. Subject Capacity

Capacity to consent will be assessed by a designated trained research staff member and/or the PI. Designated study staff will undergo individualized training with the PI in the process of capacity assessment and informed consent, in addition to all applicable research training in the capacity and consent processes available at Rush University. The study staff have experience building capacity assessments into REDCap online surveys, such that the potential participants will be prompted during the online consent process with questions to assess the participant's comprehension by asking the participant to identify key elements of the consent form, particularly the sections of the consent form that explains what specifically they are being asked to do, how long they will be involved in the study, what risks and benefits are involved, how their confidentiality will be protected, and how their data will be stored for future use.

V.c. Subject Comprehension

The study team will assess comprehension during the capacity assessments and will be available by phone to answer any questions posed by the subject. Capacity assessments will be completed online for all participants.

V.d. Debriefing Procedures

Subjects will not be debriefed about the aims and study hypotheses following administration of all study procedures due to the nature of the study and the data collected. This study does not involve deception and the aims and hypotheses are explicitly described to participants, so further debriefing is not necessary

V.e. Documentation of Consent

The consent will always be completed online and consent process details (e.g., timing) will be recorded in REDCap after built-in capacity assessments.

V.f. Costs to the Subject

There will be no cost to subjects associated with participation in this study.

V.g. Payment for Participation

Participants who attend the peer mentor training in person will be provided with parking vouchers or reimbursement for their subway/taxi travel (up to \$20). Participants who attend a focus group or interview will receive a \$50 stipend. Mentors who complete the mentor training session will receive a \$50 stipend. Finally, mentors and mentees will receive \$75 upon completion of the 8-week online survey and an additional \$75 upon completion of the 16-week final assessment online survey.

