Overview: The aims of this study are to 1) operationalize caregiving mastery in LBD, focused in fall prevention, infection and neuropsychiatric symptom management, and advanced directives; 2) test the impact of peer mentor training on LBD caregiver mastery; and 3) assess the impact of peer mentoring on LBD caregiver mentees. We will address these goals by **Aim 1**: convening focus groups with stakeholders to obtain feedback on the existing mentoring curriculum and to reflect on key areas of LBD caregiving mastery for incorporation in the revised curriculum. We will then revise the PERSEVERE curriculum and handbook based on feedback and incorporation of LBD-specific and dementia-relevant educational materials for both social support and LBD mastery education. Aim 2: To test the impact of the peer mentor training on LBD caregiver mastery, we will assess participating mentors' caregiver mastery and LBD knowledge before and after participation in an 6-7 hour mentor training session. Aim 3: The trained mentors will be matched with family caregivers of patients with LBD and complete a 16-week, structured peer mentoring program. We will compare change in caregiver mastery and LBD knowledge between baseline and 16 weeks of social support and education through mentoring calls.

Caregivers will reflect on how they successfully managed problematic patient behaviors/sudden changes, or mentor

will point out and celebrate successes, prompt caregiver on how to reinforce for future

II. Characteristics of the Research Population

experiences of others

likelihood of repetition

Responses to behavior that affect the

II.a. Number of Subjects

Total Number of Subjects: 896 total participants in four different categories: 30 focus group participants (across multiple focus groups, depending on scheduling needs), 800 participants in the online recruitment survey, 36 peer mentors, and 30 caregiver mentees

Focus group participants: 30 participants who will each participate in one focus group of up to 10 participants

Peer mentors: 36 non-professional current or former caregivers (allowing for the dropout of up to 6 mentors)

Caregiver mentees: 30 current non-professional caregivers

Online Recruitment Survey Participants: 800 current caregivers

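### Are mentees who stop mentoring early still surveyed at Week 16, or does the Aim 3 effect describe completers only?

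*Combined protocol and SAP*

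**What the plan says.** Section III.c (Aim 3) sets the final measurement: "Upon completion of the 16-week mentor program, mentors and mentees will be sent a link to complete postmentoring assessments online". For mentees that battery holds the three primary outcomes (mastery, LBD knowledge, loneliness) and the secondary scales. Section III.e, item IV, compares baseline with 16 weeks by paired t-test or Wilcoxon signed-rank test. It names no analysis population, no minimum number of calls and no rule for missing Week-16 scores. Dropout rate and reasons are reported as fidelity metrics (Figure 3 and Section III.e, item IV).

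Other passages bear on who is surveyed:

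- Section III.c starts the clock pair by pair. After the baseline battery, "The study team will then provide the mentee with contact information for their mentor", and then "Mentor-mentee pairs will then begin the 16-week peer mentor program. During this time, pairs will be expected to speak" weekly.
- Section III.d opens with "All participants who agree to be part of the study and sign the informed consent form will be asked to complete" a set of surveys.
- Section III.e, item II, expects gaps in calling: "Several topics in the revised curriculum will be repeated or given two weeks to allow for reiteration in the event of missed mentoring calls".
- The overview in Section I.c says "The trained mentors will be matched with family caregivers of patients with LBD and complete a 16-week, structured peer mentoring program", and then "We will compare change in caregiver mastery and LBD knowledge between baseline and 16 weeks of social support and education through mentoring calls".
- Reminders are described for the diaries: "Up to 3 email reminders will be sent and/or up to 3 phone calls attempted to complete each study diary". No such rule is written for the final survey.

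**The concern.** Read strictly, the link is triggered by completing the program, and a mentee who gives up in week 6 has not completed it. No passage expressly covers that person or separates stopping mentoring from leaving the study. If staff sent no link, there would be no second score, and the paired tests would drop the person without anyone having decided on a completer analysis. Counts of dropouts and their reasons would show how many left but not how they fared.

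The stake is the pilot's main product. Section II.a (Power Calculation) says the study is to supply effect sizes for sizing a larger randomized trial. A completer-only mean could be too high if people stop because mentoring is not helping, or too low if they stop because they no longer need it. A score that was never collected can be replaced only under assumptions that the data cannot test.

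**Working it through.** **The plan's own figure.** The only calculated size is for mentors (Section II.a): 30 / (1 − 0.15) = 35.3, rounded up to 36. This reproduces. The 30 mentees rest on recruitment, with no effect size, SD or dropout allowance, so there is no mentee figure to reproduce.

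**Step 1: which reading does the text support?**

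| Calendar reading (everyone at 16 weeks) | Participant reading (completers only) |
|---|---|
| III.c: the link goes to mentors and mentees, unqualified | III.c: the link follows completion of the program |
| III.c: the program is a period during which calls are expected | I.c: matched people complete a 16-week program |
| III.c: every mentee does the PDQ-Carer at the Week 8 or 10 survey, with no condition on still calling | I.c and III.e, item IV: the comparison is with 16 weeks of mentoring |
| III.d: all consented participants are asked to do assessments | I.b and II.e.1: the team describes people in its earlier program as having completed it |
| III.e, item IV: PDQ-Carer is compared from mid-study to Week 16, a time label | |
| V.g: payment depends on the 16-week survey, not on mentoring | |

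The participant reading also needs a rule for who counts as a completer, and the plan gives none. In the preceding pilot (Section I.b), those who completed had a median of 13 calls (IQR 7.5) over about 16 weeks, so completion there did not mean a full set of weekly calls. The grammatical subject of the I.c sentence is the trained mentors, and it describes the intended course, not a survey rule. The calendar reading is better supported.

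**Step 2: what would the weaker reading cost?** The inputs are assumptions. Completers change by 0.50 SD. The share stopping, f, is 0.05 (low case), 0.15 (the plan's mentor figure) or 13/48 = 0.271 (the preceding pilot, where 35 of 48 had finished to date; an upper bound, because that program was still running). Stoppers change by 0 or by 0.80 SD.

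All-starter mean = (1 − f) × 0.50 + f × stopper change.

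| f | All-starter mean, stoppers 0 | Completer mean minus this | All-starter mean, stoppers 0.80 | Completer mean minus this |
|---|---|---|---|---|
| 0.05 | 0.475 | +0.025 | 0.515 | −0.015 |
| 0.15 | 0.425 | +0.075 | 0.545 | −0.045 |
| 0.271 | 0.365 | +0.135 | 0.581 | −0.081 |

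**Step 3: compare with sampling error.** The 95% half-width is t(0.975, n − 1) / √n with an SD of change of 1: 0.373 for 30 pairs, 0.404 for 26 and 0.443 for 22. The worst shift is 0.135 / 0.443 = 0.30 of the half-width. At 15% stopping it is 0.075 / 0.404 = 0.19.

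**Step 4: can this be turned into a sample-size factor for the later trial?** With n proportional to 1/d², stoppers at 0 and f = 0.271, the factor is (0.50 / 0.365)² = 1.88. That treats a single-arm pre-post change as a between-arm difference, which holds only if future controls do not change. If controls change by −0.2 SD, the factor is (0.70 / 0.565)² = 1.54; if by +0.2 SD, it is (0.30 / 0.165)² = 3.32 (from unrounded values). The documents give nothing on control change, so no such factor is a finding about this plan.

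**The case for a change.** The strongest case for acting is that the silence on early stoppers is real, the loss cannot be undone once Week 16 has passed, and one sentence would prevent it. The team's own usage lends the participant reading some weight: Section I.b counts those who have completed the earlier program, and Section II.e.1 requires former mentors and mentees to have completed 16 weeks of mentoring. Section III.c specifies every mentee for the mid-study PDQ-Carer but does not repeat that for the final battery. Section III.d gives no time point, and payment for a survey does not settle who is sent it. A confidence interval reflects sampling error only and would not reveal selection.

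Much of this stands as a remark on drafting: the ambiguity exists, and the arithmetic is right on its assumptions. It does not show that stoppers will be left out. The II.e.1 wording is an eligibility rule for focus groups and says nothing about sending surveys. Nor would rewriting the analysis section gain anything, since the paired tests already use everyone with both scores and set no call threshold. Mentees who leave the study altogether would lack a Week-16 score under any wording. The consent form was not available here, so it cannot be ruled out that it covers early stopping.

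**Conclusion.** The concern does not call for a change. This is a missing detail that a study team fills sensibly by sending the Week-16 link to each pair 16 weeks after it starts, whether or not the calls have continued. That is what the text as a whole best supports, and under it the Aim 3 analysis already covers every mentee who returns both surveys.

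Harm arises only on the weaker reading, and then only if stoppers differ from completers. Under the assumptions used (completer change 0.50 SD, stopping rates from 5% to 27%, stopper change 0 or 0.80 SD, equal SDs), the completer mean would be off by between −0.081 and +0.135 SD, at most about a third of the 95% half-width in a pilot sized on recruitment. The mentee stopping rate, the effect size and the stopper outcomes are all assumed, so neither the size nor the direction of any bias can be taken from the documents. Mentor post-mentoring outcomes share the same trigger and the same answer; the Aim 2 comparisons before and after training do not depend on it.
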